**Source of subjects and recruitment methods:**

Participants will be recruited from community flyers and announcements at HIV focused community centers, community newspaper advertising, and referrals from infectious disease physicians and primary care physicians familiar with the study. Recruitment may also be done via RSVP for Health and/or internet announcements such as Partners “All User Broadcast.” Potential participants, from all referral sources, will contact the study investigator directly by phone for a pre-study evaluation via telephone to determine eligibility.

**IV. Subject Enrollment**

Informed consent will be obtained at the screening visit by a licensed physician or nurse practitioner, prior to any procedures or interventions. Potential research subjects will have the entire protocol explained in detail and study investigators will review the consent form item by item, answering any and all questions. Once risks and benefits have been reviewed and subjects have agreed to participate by signing the consent, the screening visit will continue as described in the subject selection section. Once final eligibility has been determined subjects will be scheduled for a baseline visit.

**Treatment assignment and randomization:**

During the baseline visit randomization will be done. All subjects will receive lifestyle modification as described below. Subjects will be randomized to receive eplerenone 50mg po qd or identical placebo for 6 months. Doses will start at 25mg for the first week to avoid hypotension. The study will be double-blind. Randomization will be stratified by

Randomized placebo-controlled trial to investigate the effects of eplerenone in patients with HIV-associated abdominal fat accumulation

gender, age (>45 y), and BP (SBP>140 or DBP>90 vs. normotensive). After the first 6 months, open-label eplerenone will be given for 6 months in all patients, and lifestyle modification will continue. During the open-label period all subjects will start eplerenone 25 mg a day for 1 week and dose will be increased to 50 mg a day at the 25 week safety visit to maintain blinding.

Prior to randomization in all cases, the subject's primary care physician will be consulted regarding the appropriateness of the protocol including the lifestyle modification program. Subjects are not eligible if they do not meet all of the enrollment criteria

## **V. Study Procedures**

### Data Collection/Study Procedures

#### *Screen Visit (to determine eligibility)*

1. Informed consent; history and PE, vital signs including blood pressure, and urine pregnancy test for all female subjects
2. Bionutrition: Height, metabolic weight, and anthropometric measurements, including waist and hip circumferences, distribution of a 4-day food record
3. Fasting blood: potassium, creatinine, CBC, ALT, FSH (women only)
4. 2 hour oral glucose tolerance test

Prior to the baseline, 3, 6 and 12 month visits, subjects will go on a uniform 200 meq/day sodium diet.

#### Baseline, 6 months, and 12 months:

1. Urine pregnancy test of all female subjects
2. MRI/MRS for abdominal visceral adipose tissue, subcutaneous adipose tissue, liver fat, intramyocellular lipid content
3. Flow mediated vasodilation
4. Bionutrition: DEXA, REE, anthropometric measurements and review of a session in the lifestyle modification workbook
5. Fasting blood will be drawn for CBC, lipid profile, HgbA1c, chem 7, ALT, CD4/8, HIV viral load, aldosterone, plasma renin activity, inflammatory markers and adipokines: MCP-1, CRP, adiponectin, PAI-1, resistin, TNF $\alpha$ , TNFR2, IL-6, SHBG, total and free testosterone, LH, FSH, estradiol (females only).
6. 24 hour urine will be collected for aldosterone, potassium, sodium, cortisol and creatinine
7. Euglycemic hyperinsulinemic clamp
8. Interval medical history and physical exam including blood pressure check
9. Modifiable activity questionnaire
10. Overnight q 20 minute sampling for GH pulsatility analysis.

#### Interim Safety Visits 1 wk, 2 wks, 4 wks, 2 months and same schedule post 6 month crossover with an additional visit at 10 months

1. Physical exam and interval medical history including blood pressure check
2. Blood: creatinine, K, CBC, ALT
3. Urine pregnancy test of all female subjects

#### 3 Month Visit

1. Urine pregnancy test for all female subjects
2. Physical exam, including blood pressure check, and medical history

Randomized placebo-controlled trial to investigate the effects of eplerenone in patients with HIV-associated abdominal fat accumulation

3. Euglycemic hyperinsulinemic clamp
4. Bionutrition: DEXA, anthropometric measurements, and review of a session from the lifestyle modification workbook.
5. Fasting blood: lipid profile, HgbA1c, chem. 7, CBC, potassium, creatinine, ALT, CD4/8, viral load, aldosterone, plasma renin activity, inflammatory markers and adipokines: MCP-1, CRP, adiponectin, PAI-1, resistin, TNF $\alpha$ , TNFR2, IL-6, SHBG, total and free testosterone, LH, FSH, estradiol (females only).
6. 24 hour urine will be collected for aldosterone, potassium, sodium, cortisol, and creatinine
7. Optional overnight q 20 minute sampling for growth hormone pulsatility analysis
8. Modifiable activity questionnaire

Oral Glucose Tolerance Test: A standard 75g OGTT will be performed on the morning of the screen visit following a 12 hour fast, with interval measurements of insulin and glucose at 0 and 120 min.

Euglycemic-Hyperinsulinemic Clamp: After 12-h overnight fast, patients will receive a primed infusion of regular insulin mixed with albumin, 80 mU/m^2, for 2 hours, with a variable rate of dextrose administered to maintain blood glucose at 5.0 mmol/L (90 mg/dL). Blood samples will be collected for glucose at time 0 and every 5 min during the 2-hour clamp, and samples for insulin will be collected every 20 min from 0-120 minutes. Insulin sensitivity will be calculated.

Optional GH Pulsatility Analysis: Starting at 2000 until 0740 the next morning, fasting blood will be sampled every 20 minutes. Approximately 1.5cc of blood will be drawn at each time point for a total of 54cc. Mean overnight GH concentration, basal concentration, pulse frequency, pulse amplitude and overall pattern regularity will be determined using the deconvolution analysis and cluster computerized pulsatility program.

H Magnetic Resonance Spectroscopy & MRI Scanning: After 12-hour overnight fast subjects will undergo H -MRS of the calf muscle and of the liver. For calf muscle H -MRS, voxel measuring 15 x 15 x 15 mm (3.4 ml) will be placed on the axial T1-weighted slice with largest muscle cross-sectional area of the tibialis anterior and subsequently the soleus, avoiding visible interstitial tissue, fat or vessels. Single-voxel H -MRS data were acquired using point-resolved spatially localized spectroscopy pulse sequence. For liver H-MRS, a breath-hold true fast imaging with steady precession sequence will be obtained. A voxel measuring 20 x 20 x 20 mm (8 ml) will be placed within the right lobe of the liver, avoiding vessels or artifact. Breath-hold single-voxel H -MRS data will be acquired using point-resolved spatially localized spectroscopy pulse sequence without water suppression with the following parameters: TE of 30 msec, TR of 1500 msec, eight acquisitions, 1024 data points, and receiver bandwidth of 2000 Hz. For abdominal visceral and subcutaneous fat areas, conventional MR images will be acquired for anatomic reference of H-MRS overlays. Image series will include Axial T1-weighted localizers. A single axial slice of the abdomen and mid thigh will be obtained with magnetic resonance imaging. Abdominal visceral and subcutaneous fat areas, as well as mid thigh subcutaneous fat area will be determined based on offline analysis of tracings obtained utilizing commercial software. No intravenous contrast will be used. The total amount of time in the magnet will be approximately 1 hour.

Randomized placebo-controlled trial to investigate the effects of eplerenone in patients with HIV-associated abdominal fat accumulation

Flow Mediated Vasodilation: After a 12 hour overnight fast a blood pressure cuff will be inflated to 50 mmHg above systolic blood pressure (or 250 mmHg, whichever is less) for five minutes. The diameter of the brachial artery will be recorded by ultrasound under no-flow conditions and over a five minute period after the cuff is deflated (reflow). The images will be recorded for analysis of the time-course and extent of dilation of the brachial artery.

Whole Body Dual Energy X-ray Absorptiometry (DEXA)

DEXA (Hologic) will be used to determine whole body and regional fat will be assessed. The technique has a precision error (1 SD) of 3% for whole body fat and 1.5% for lean mass. It estimates body composition from the attenuation of X-rays pulsed in synchrony between 100 and 140 kV with the line frequency for each pixel of the scanned image. (As an external standard for analysis of body composition, a step phantom, with six fields of acrylic and aluminum of varying thickness and known absorptive properties, was scanned periodically for calibration.) The DEXA scan will be used to determine total body fat as well as regional body fat measurements.

Anthropometric Measurements

Subjects' height and weight will be obtained and plotted on standard weight charts to determine percent of ideal body weight. Body mass index will be calculated. Anthropometric measurements of waist to hip ratio, leg circumference, arm circumference and neck circumference will be performed using a standardized technique. Waist-to-hip ratio will be determined from the circumferential measurements of the iliac waist and the hips at the level of the iliac crest taken with the patient in an upright standing position.

Bionutritional Analysis: Protein, carbohydrate, fat, micronutrient, dietary supplements and alcohol intake will be determined from 4-day food records (3 weekdays and 1 weekend day) (Nutrition Data systems).

High Sodium Diet: A high sodium diet will be followed for 6 days prior to the Baseline, 3, 6 and 12 month visits and consists of the subject's normal, ad lib diet supplemented with high sodium meals and/or chicken broth, and snacks to equal approximately 200 mEq of sodium. The 7th day (last day) of the high sodium diet will be completed on the first day of the Baseline, 3, 6 and 12 month visit.

Lifestyle Modification: Goals derived from the AACE and NCEP-ATP III guidelines and the Diabetes Prevention Program are as follows: <35% calories from fat, < 7% calories from saturated fat, up to 10% calories from polyunsaturated fat, reduction of trans fatty acid intake, up to 20% calories from monounsaturated fat, and 25-35g of fiber per day. 3 hrs of physical activity/week at moderate intensity, >10,000 steps in daily activity, measured by pedometer. The curriculum is modeled after the Diabetes Prevention Program. Subjects will complete lifestyle sessions in the offices of the Program in Nutritional Metabolism, the Clinical Research Center at MGH or by phone conversation with protocol study staff trained to implement the curriculum. The curriculum will be introduced and reinforced with weekly sessions during wks 0-24 (see **Table**), then continued with monthly sessions after open label extension. There will also be \$100 per patient allowance that will be used in individualized ways to promote lifestyle goals: For example, subsidizing a gym membership, purchasing of relevant cookbooks or purchase

Randomized placebo-controlled trial to investigate the effects of eplerenone in patients with HIV-associated abdominal fat accumulation

of appropriate food items from health food stores, etc.

Session	Topic	Initial Session	Reinforcement
1	Welcome to the Lifestyle Balance Program	Week 1	Week 13
2	How to Read a Nutrition Label	Week 2	Week 14
3	The Components of a Healthy Diet	Week 3	Week 15
4	Things to Know Before Becoming Active	Week 4	Week 16
5	Living on Active Lifestyle	Week 5	Week 17
6	Focus on Fiber	Week 6	Week 18
7	Whole Grains	Week 7	Week 19
8	Fats & Cholesterol	Week 8	Week 20
9	Fruit, Vegetables & Milk	Week 9	Week 21
10	Fish Meat, Poultry, Eggs, Peas & Beans	Week 10	Week 22
11	Tips for Health Eating Out	Week 11	Week 23
12	Food Safety	Week 12	Week 24
13	Appendix-printable fact sheets and logs		

## VI. Biostatistical Analysis

The primary endpoint will be change in insulin stimulated glucose uptake as measured by euglycemic clamp. Secondary endpoints include change in levels of adipokines and endothelial function. In addition, we will assess eplerenone's effects on hepatic fat and IMCL. VAT and SAT will be measured simultaneously and controlled for in the analyses of hepatic fat and IMCL. Randomization will be stratified by gender, age (< or > 45), and BP (SBP >140 or DBP>90, or normotensive). Wilk-Shapiro test will be used to assess for normality of distribution of all variables, and variables that are not normally distributed will be log-transformed. Baseline variables will be compared between treatment groups by t-test for continuous variables and Wilcoxon Rank Sum test for variables that are not normally distributed. Any baseline variable that is statistically different between treatment groups will be adjusted for in subsequent analysis. We will analyze the entire set of repeated measurements (baseline, 3 and 6 mos) by using the longitudinal mixed effects model, using all available data, including interim data from those who do not complete the study, to determine differences in longitudinal mean changes between eplerenone and placebo over 6 mos of treatment (i.e., test for time x group interaction). The analyses will be intention to treat, using all interim data for subjects who do not complete the study. We will control for gender, race, anti-hypertensive and lipid lowering medication use, urine free cortisol, dietary intake (caloric, macronutrient, alcohol, supplements, salt intake), activity, ARV use and smoking. We will analyze the dietary data in terms of overall caloric intake and macronutrient composition, to determine whether there are any differences in diet by study treatment, or whether change in dietary intake patterns, including vitamins, affects the treatment results. Similar analyses will be performed for activity using the Modifiable Activity Questionnaire. In a sensitivity analysis if the dropout rate is higher than expected or differs between groups, we will

Randomized placebo-controlled trial to investigate the effects of eplerenone in patients with HIV-associated abdominal fat accumulation

use a LOCF approach carrying forward the last available data to use in the analysis, to determine if the dropouts affected the results. All patients cross-over to open label eplerenone from mos 6 to 12. The primary analysis will be the comparison of placebo and eplerenone after 6 months and the purpose of the open label design after 6 mos is to encourage recruitment and retention. Safety data will be collected at all time points and continued treatment over 12 mos will allow us to determine safety and tolerability over one year and whether changes in critical endpoints continue to improve with one year of dosing.

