appears to play a crucial role in adipocyte differentiation and lipid accumulation. In 3T3-L1 cells, MR but not glucocorticoid receptor (GR) downregulation by siRNAs inhibited adipocyte differentiation and decreased cell triglyceride content [44]. Furthermore, whereas murine adipocytes lacking GR show mild impairment in lipid accumulation during early differentiation, adipocytes lacking MR demonstrate failure to accumulate lipid throughout differentiation [39]. These observations are supported by *in vivo* models of ob/ob and db/db mice, in which MR blockade with eplerenone significantly decreased the number of hypertrophic adipocytes in epididymal fat [45]. Blockade of MR, which we propose to study in this grant application, would block MR activation by cortisol as well as aldosterone in adipose tissue, and may decrease lipid accumulation and ultimately affect body composition. There is also some evidence to suggest that MR blockade may affect hepatosteatosis, which is prevalent in HIV-infected individuals in association with increased abdominal adiposity [46, 47]. In a murine model of diet induced obesity, Wada et al. demonstrate that spironolactone significantly decreases hepatic triglyceride accumulation as well as decreasing serum triglyceride, total cholesterol, and free fatty acid [20]. In humans, Fallo et al. demonstrate an increased prevalence of hepatosteatosis in patients with primary aldosteronism (PA) compared to normotensive controls, but the prevalence in PA (57.5%) was not different from the prevalence found in a matched cohort with low-renin essential hypertension (55.8%) [48]. Further studies are clearly needed to determine whether mineralocorticoid activity affects hepatic triglyceride accumulation. Aim I of the current proposal will investigate relationships between aldosterone level and body fat distribution, including ectopic fat storage in liver.

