## Randomized placebo-controlled trial to investigate the effects of eplerenone in patients with HIV-associated abdominal fat accumulation

proven safe and effective in non-HIV infected populations with cardiovascular disease. Our preliminary data suggest increased aldosterone in HIV-infected individuals with increased abdominal adiposity, a population with significant risk of insulin resistance and cardiovascular morbidity and for whom no specific treatment is currently available. MR blockade with eplerenone may be one beneficial strategy to address impaired glucose homeostasis and cardiovascular risk in this group, but the effects of eplerenone in HIV-infected individuals with abdominal fat accumulation and impaired glucose tolerance are not known. We hypothesize that by blocking the effects of increased aldosterone secretion, eplerenone treatment will significantly improve insulin sensitivity in this population and may also decrease visceral adipose tissue, and improve dyslipidemia and inflammation, thereby improving vascular function. In a 6-month, randomized, placebo-controlled study followed by 6-month open-label extension, we will test for the first time the effects of the selective mineralocorticoid blocker, eplerenone, on markers of insulin sensitivity, dyslipidemia, body composition, inflammation and vascular function in this population.

Eplerenone was chosen for this study instead of an ACE-I or Angiotensin II Receptor Blocker (ARB) because we want to specifically test the effects of MR blockade, including in tissues in which cortisol may activate the MR due to lack of significant 11 $\beta$ HSD2 expression. Evidence suggests that MR activation in adipose tissue may affect adipocyte differentiation and triglyceride accumulation, and cortisol may act similarly to aldosterone at the MR in this regard. As we aim to determine the effects of MR blockade on cardiometabolic parameters and body composition, specifically VAT accumulation, we have chosen eplerenone in order to block the effects of both aldosterone and potentially cortisol at the MR. Eplerenone was chosen rather than spironolactone because eplerenone is more selective for the MR, does not affect adrenal steroid synthesis as spironolactone does, and has a better side effect profile.

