### II. Specific Aims

To determine if mineralocorticoid receptor blockade with eplerenone among HIV-infected patients with increased waist circumference and impaired glucose tolerance will ameliorate cardiovascular risk parameters, we will perform a randomized double-blind study of eplerenone vs. placebo for 6 months, with a 6 month safety extension. We will provide all subjects with lifestyle modification throughout the study. We hypothesize that addition of eplerenone to lifestyle modification will significantly:

- A. Improve insulin sensitivity as measured by euglycemic hyperinsulinemic clamp.
- B. Improve endothelial function and adipokines.
- C. Reduce critical measures of adiposity, including liver fat and IMCL

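### Liver fat and IMCL are adjusted for VAT and SAT from an unstated visit; if month-6 values are used and eplerenone lowers VAT, the total effect asked for in Aim C is not estimated

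*Combined protocol and SAP*

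**What the plan says.** Section VI (Biostatistical Analysis) names the primary clamp endpoint and the secondary endpoints, then adds: "In addition, we will assess eplerenone's effects on hepatic fat and IMCL". The next sentence sets the adjustment: "VAT and SAT will be measured simultaneously and controlled for in the analyses of hepatic fat and IMCL". It does not say whether the covariate is the baseline value, the month-6 value, the change, or a time-varying value.

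The general model in the same section is a mixed model with a time x group test, used "to determine differences in longitudinal mean changes between eplerenone and placebo over 6 mos of treatment". Its covariate list does not include VAT or SAT. The VAT/SAT sentence is specific to liver fat and IMCL, so it governs them. The only sensitivity analysis named is LOCF for dropout.

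Other relevant places:

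- Section V, schedule for baseline, 6 and 12 months, has a single item: "MRI/MRS for abdominal visceral adipose tissue, subcutaneous adipose tissue, liver fat, intramyocellular lipid content". The 3 Month Visit lists no MRI/MRS, and all patients take open-label eplerenone from month 6.
- Section II, Aim C, hypothesises that adding eplerenone will "Reduce critical measures of adiposity, including liver fat and IMCL".
- Section I, Conclusion, hypothesises that eplerenone "may also decrease visceral adipose tissue" and explains the choice of drug by the wish to determine the "effects of MR blockade on cardiometabolic parameters and body composition, specifically VAT accumulation".
- Section I, on aldosterone, the mineralocorticoid receptor (MR) and adipose tissue, says MR blockade "may decrease lipid accumulation and ultimately affect body composition".

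**The concern.** If *simultaneously* means the same scan as the outcome, the follow-up covariate is month-6 VAT and SAT, measured after randomisation. The protocol's own rationale is that the drug may lower VAT. It also describes hepatosteatosis as going together with abdominal adiposity. VAT is then a possible step on the path from drug to liver fat.

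Two things follow if eplerenone does lower VAT:

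- **A real effect is understated.** The part of the liver-fat or IMCL effect that runs through VAT is removed from the group term. Aim C asks whether eplerenone reduces these measures, with no qualifier about an effect independent of VAT.
- **A null effect can look like harm.** If there is no liver-fat effect but VAT and liver fat share an unmeasured cause, the adjusted test rejects too often, almost always in the direction of apparent harm.

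An unstated visit also leaves the choice open until after the data are seen.

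**Working it through.** **The plan's own figure.** The Sample Size Calculation gives 80% power for 0.8 SD with 25 evaluable patients per group. Taken as two-sided 5%, this reproduces: 80.7% by the normal approximation and 79.1% by the exact t (48 df). It concerns glucose uptake; no power is given for liver fat or IMCL.

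**Which visit?** MRI/MRS is scheduled at baseline, 6 and 12 months. Month 3 has none, and month 12 is open-label. So the randomised comparison has two scans, baseline and month 6, and a concurrent covariate at follow-up can only be the month-6 value.

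**Inputs.** From the documents: 25 per arm, and 0.8 SD borrowed from the clamp endpoint as the true liver-fat reduction. Assumed, because the documents give none: VAT lowered by a = 0.3 to 0.7 SD; slope of liver fat on VAT b = 0.3 to 0.6 (SD per SD); baseline to 6-month correlation r = 0.6, varied to 0.4 and 0.8; complete data; two-sided 5%. SAT is not modelled, because the documents make no prediction for it.

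**Model 1: month-6 liver fat on group, baseline liver fat and VAT.** With month-6 VAT the expected estimate is

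0.8 − a × b × (1 − r²) / (1 − r² × b²).

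At r = 0.6:

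- a = 0.3, b = 0.3: 0.8 − 0.09 × 0.64 / 0.9676 = 0.74
- a = 0.5, b = 0.5: 0.8 − 0.25 × 0.64 / 0.91 = 0.62
- a = 0.7, b = 0.6: 0.8 − 0.42 × 0.64 / 0.8704 = 0.49

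**Model 2: Section VI's time x group mixed model** on the two scans, random intercept, VAT time-varying. The simulated estimates lie close to 0.8 − a × b; for example, 0.8 − 0.7 × 0.6 = 0.38.

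Simulated estimate (SD) and power, with 20,000 runs per cell for model 1 and 6,000 for model 2:

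| a, b | Model 1, month-6 VAT | Model 2, time-varying VAT |
|---|---|---|
| 0.3, 0.3 | 0.74, 89% | 0.71, 81% |
| 0.3, 0.6 | 0.67, 90% | 0.62, 84% |
| 0.5, 0.5 | 0.62, 80% | 0.55, 68% |
| 0.7, 0.3 | 0.66, 77% | 0.59, 62% |
| 0.7, 0.6 | 0.49, 63% | 0.38, 42% |
| Comparator | 0.80, 92–93% (baseline VAT) | 0.80, 87–88% (no VAT or baseline VAT) |

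**Sensitivity to r (model 1), at the mildest and strongest cells.** At r = 0.4 the estimates are 0.72 and 0.43 SD with power 78% and 44%, against 84% with baseline VAT. At r = 0.8 they are 0.77 and 0.61 SD with power 99% and 93%, against 99%.

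**Where power does not fall.** With b = 0.6 and VAT lowered by 0.2 SD, power is 94% against 93% in model 1 and 90% against 87% in model 2, although the estimates are still reduced (0.71 and 0.68 SD). If VAT is unchanged, the estimate stays at 0.80 SD and power is 98% and 97%.

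**No liver-fat effect, shared unmeasured cause (model 1, r = 0.6).** With VAT lowered by 0.5 SD:

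- VAT–liver fat correlation 0.36: 8.0% rejections (7.3% apparent harm, 0.7% benefit); apparent increase 0.12 SD.
- Correlation 0.6: 18.6% rejections (18.4% harm, 0.2% benefit); apparent increase 0.22 SD.

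With baseline VAT the total stays at about 5%. The nominal rate on each side is 2.5%, so false benefit becomes rarer, not more common.

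**The case against.** The bias needs two conditions: month-6 values must be meant, and eplerenone must lower VAT. *Simultaneously* may only describe how the scan is acquired, and Section I says only that the drug may lower VAT. This is fair, and it is why the conclusion is conditional. But nothing in the text points to baseline, and leaving the visit open is itself a defect.

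Controlling for concurrent VAT can answer a legitimate question: does eplerenone affect ectopic fat beyond its effect on abdominal fat? That is so, but the plan neither labels the analysis as mechanistic nor pairs it with a total-effect analysis, and Aim C does not ask that question.

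The stakes are limited. Liver fat and IMCL come after the primary and secondary endpoints and are not powered. This stands.

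The figures are illustrative, and the range starts at VAT lowered by 0.3 SD. With VAT lowered by 0.1 to 0.2 SD and slope 0.3, model 1 gives 0.78 to 0.76 SD and power of 93% to 91%, against 92%: almost no loss. This also stands. The values of 0.49 and 0.38 SD are ends of an assumed range, not predictions.

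A month-6 comparison would replace the mixed model for these outcomes. With only two scans in the randomised period this matters little. Diet, activity, urine free cortisol and medication covariates also lack a stated visit; that is true, but it does not settle the VAT/SAT question.

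**Conclusion.** The concern holds. The plan commits the liver fat and IMCL analyses to an adjustment whose visit is not stated, with no analysis named without it. On the more natural reading it conditions on a variable the protocol expects treatment may change, so the group term is not the total effect in Aim C.

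The size cannot be fixed from the documents. Under the assumptions above, a true 0.80 SD reduction is reported as about 0.74 to 0.49 SD in model 1 and 0.71 to 0.38 SD in model 2. If baseline values were meant there is no bias. If eplerenone changes neither VAT nor SAT there is none either, and the adjustment gains power. The primary clamp comparison and its sample size are not affected. The point should be fixed; confidence is medium because it turns on an ambiguous sentence.

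**What to change.** In Section VI, make the main liver fat and IMCL analysis the 6-month comparison between arms, adjusted only for values obtained before randomisation: the baseline value of that outcome, the stratification factors and, if wanted, baseline VAT and SAT. Keep any model with concurrent VAT and SAT as a labelled exploratory analysis of mechanism. If baseline VAT and SAT were always intended, state this in the VAT/SAT sentence.

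The cost is SAP wording only. Baseline VAT, SAT, liver fat and IMCL are already collected under Section V, no new data are needed, and the concurrent-adjusted model can still be run.

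### The analysis adjusts for whichever baseline variables happen to differ significantly between arms, and its covariate list omits two of the three stratification factors (age group and BP stratum)

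*Combined protocol and SAP*

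**What the plan says.** Section VI (Biostatistical Analysis) compares baseline variables between arms by t-test or Wilcoxon test, and then states: "Any baseline variable that is statistically different between treatment groups will be adjusted for in subsequent analysis". It does not say which variables are tested, at what level, or whether an added variable enters as a main effect or crossed with time.

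The primary model is described as follows: "We will analyze the entire set of repeated measurements (baseline, 3 and 6 mos) by using the longitudinal mixed effects model". The test is of time by group, and "The primary analysis will be the comparison of placebo and eplerenone after 6 months".

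The same section has a fixed covariate list, beginning "We will control for gender, race, anti-hypertensive and lipid lowering medication use, urine free cortisol, dietary intake" and ending with antiretroviral use and smoking. On stratification, Section VI says "Randomization will be stratified by gender, age (< or > 45), and BP (SBP >140 or DBP>90, or normotensive", and Section IV (Treatment assignment and randomization) gives the same factors: "gender, age (>45 y), and BP (SBP>140 or DBP>90 vs. normotensive". Gender is on the covariate list. Age and BP stratum are not. Anti-hypertensive medication is listed, but it is only a partial stand-in for the BP stratum.

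**The concern.** After proper randomisation a significant baseline difference is a chance event. A rule triggered by significance therefore picks covariates for being imbalanced, whether or not they predict the change in glucose uptake, and the primary model cannot be written down until the baseline data are seen. The pool may be large: the baseline visit in Section V includes, among much else, "inflammatory markers and adipokines: MCP-1, CRP, adiponectin, PAI-1, resistin", and also the "Euglycemic hyperinsulinemic clamp", whose baseline value is itself a response in the planned model.

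The strata raise the opposite problem. They are known in advance and balanced by design, so the analysis should normally reflect them, and a rule triggered by imbalance will almost never bring them in. With 25 evaluable patients per arm and about 80% power, a few points either way are worth having when they cost almost nothing.

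**Working it through.** **1. The plan's own power figure.** Inputs from Sample Size Calculation: 25 per arm, 0.8 SD, P = 0.05 (taken as two-sided), t-test. The non-centrality is 0.8 × √(25/2) = 2.83. With 48 df and critical value 2.011, power is 79.1% (80.7% by the normal approximation). The stated 80% is reproduced.

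**2. Size of the pool.** Section VI names none. Counting each panel once in the baseline list of Section V: MRI/MRS 4, flow-mediated dilation 1, DEXA/REE/anthropometry 3, blood 23, urine 5, clamp 1, BP 1, activity 1, GH 1, total 40. Removing urine cortisol and activity, which are already listed covariates, leaves 38. I use K = 20 to 38 as an assumed range, with each test at 0.05.

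**3. How often the rule fires.** For independent candidates the chance is 1 − 0.95^K: 64% at K = 20 and 86% at K = 38. At pairwise correlation 0.5, simulation gives 42% and 56%.

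**4. Entered as main effects.** A time-constant covariate acts on the between-subject level, while time by group is a within-subject contrast. In test data sets with complete follow-up, the 6-month estimate and SE were identical with and without the covariate (for example 1.748, SE 0.399, both ways). With about 20% missing at 6 months they moved by less than 0.01. Simulated power with 13 listed main effects and K = 38 was 79% with or without the rule, and 75% with or without it at 15% dropout.

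**5. Entered with time, or in a change-score model.** One non-prognostic variable exactly at p = 0.05 has variance inflation 1 + 2.011²/48 = 1.084. The non-centrality falls to 2.83/√1.084 = 2.72 and power to 75.8%. Averaged over simulated trials, with non-prognostic candidates and no listed covariates:

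| Candidates | Without rule | Rule, independent | Rule, correlation 0.5 |
|---|---|---|---|
| 20 | 79.1% | 74.4% | 76.5% |
| 38 | 79.1% | 70.3% | 75.2% |

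The loss is about 5–9 points if candidates are independent and about 3–4 at correlation 0.5. With 1 to 20 of 20 candidates prognostic, the net loss against no adjustment was about 1.5–3.5 points. Type I error under the rule stayed at about 5% with non-prognostic candidates and was slightly below 5% with prognostic ones.

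**6. When the trigger is prognostic.** Take the baseline clamp value as the only candidate in a change-score model, with within-subject correlation 0.5. Among trials where it triggers, the rule cuts false positives from about 17–18% to 4% and raises power from about 67–69% to 85–86%. Over all trials, power is 79% without the rule, 80% with it and 89% if baseline is prespecified. At correlation 0.7 prespecifying gives 84%. With one such variable (correlation 0.5 with change) among 20 tested, power is 88% prespecified, 78% unadjusted and 75% under the rule.

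**7. The omitted strata.** With assumed age, sex and BP distributions and blocks of 4, the rule flags the age stratum in 0% of trials, the BP stratum in 0.06% and continuous age in 0.5%. If balanced strata explain a share R² of the variance of the change and are left out, type I error is roughly 2[1 − Φ(1.96/√(1 − R²))], which is 4.4%, 3.9% and 2.8% at R² 5%, 10% and 20%. Simulation without listed covariates (blocks of 4 in 8 strata, or exact balance) agrees:

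| R² | Type I error, omitted | Power, omitted | Power, included |
|---|---|---|---|
| 0% | 5.0–5.1% | 79.1% | 78.9% |
| 5% | 4.5% | 79.4% | 80.7% |
| 10% | 3.8–4.0% | 79.9% | 82.5% |
| 20% | 2.8–3.4% | 81.1% | 87.0% |

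**The case against.** The strongest reply is that Section VI describes a time by group mixed model and never mentions covariate by time terms. Main effects are then the natural reading, and step 4 shows no loss of power. That stands. The power losses in step 5 depend on a form of entry the plan does not state and on a pool it does not name. The upper end also needs 38 independent candidates, although many of the measures overlap biologically, estradiol is for women only, and GH sampling is called optional at 3 months and under Risks and Discomforts. The main-effects reading does not rescue the rule, however, because the rule then has no effect on the contrast it is meant to protect.

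Several stronger readings are tempting and are not supported:

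- **The rule inflates false positives or invites selection on results.** The trigger uses baseline data only, and type I error stays at or below about 5%.
- **The rule can only do nothing or cost power.** Step 6 shows that it helps when a strongly prognostic variable triggers it.
- **A chance baseline-clamp imbalance is harm done by the rule.** When that variable triggers (5% of trials, mean imbalance 0.65 SD), the change contrast shifts by about 0.65 × (1 − within-subject correlation): 0.32 SD at 0.5 and 0.20 SD at 0.7. This comes from using change from baseline. It is there with or without the rule.
- **The trial is really powered at 65%.** That figure arises only if 13 listed covariates enter with time or in a change-score model and predict nothing. It describes the list, which this point leaves alone.

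**Conclusion.** The point holds as a correctable weakness in the analysis plan and is no threat to validity. The rule selects on chance imbalance. As main effects it corrects nothing. Crossed with time or in a change-score model it costs about 3–4 points of power at pairwise correlation 0.5 and 5–9 if candidates are independent, given 20–38 mostly non-prognostic candidates and no listed covariates. Where it helps, prespecified adjustment helps more.

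The missing strata matter only if age and BP predict the change in glucose uptake. At R² of 5–10%, including them gains about 1–3 points and removes a mild conservatism. The 20% row is an upper illustration, and nothing in the documents supports a value that high. Pool size, correlations, R², block size and the 0.05 trigger level are all assumptions.

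**What to change.** Remove the significance-triggered adjustment from the primary analysis. Report baseline characteristics by arm without significance tests, and keep any adjustment for a chance imbalance as a labelled sensitivity analysis that does not replace the primary result.

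Add age group and BP stratum, as randomised, alongside gender, in a form that can affect the tested contrast, and state which of these applies:

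- stratum by time terms, if baseline stays a response; or
- main effects together with the prespecified baseline clamp value, if change or post-baseline values are the response.

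The second form also removes the effect of a chance baseline-clamp imbalance. The first does not. State also how the listed covariates enter. The rest of that list, and the VAT/SAT adjustment for hepatic fat and IMCL, need not change on this account.

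The cost is one sentence replaced and one added. For the two strata it is two degrees of freedom in a change-score model, or two main effects and four interaction parameters in a three-visit model with categorical time. If age and BP are not prognostic there is no gain, and 0–1 point of power is lost (79.1% to 78.9% without listed covariates).
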